10.4.2. Sample Size Justification

We calculated power using a one-sample proportion test to determine if a population proportion is significantly different from hypothesized value. We define our hypotheses as:

Null hypothesis (H_0) that the proportion is $P_0 = 0.5$

Alternative hypothesis (H_1) that the proportion is $P_1 = 0.8$.

To test our hypothesis of clinical improvement:

$$H_0: P \leq P_0 \text{ vs } H_1: P = P_1 > P_0$$

Our sample size of 20 achieves 100.0% power to detect a difference ($P_1 - P_0$) of 0.3 using a one-sided exact test at an alpha level of 0.05. The results assume that population proportion under the null hypothesis is 0.5. Power was also computed using the normal approximation method.

10.4.3. Effect Size Justification

The null hypothesis efficacy rate (CBR at 1 year) of 50% at 1 year is based on clinical experience at Stanford where desmoid tumors that are subtotally treated with cryoablation have > 50% chance of recurrence at 1 year; determined using mRECIST.

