1.1. Study Rationale

In this trial, we propose the combination of systemic therapy with nirogacestat and cryoablation to maximize the benefits of both modalities for subjects with growing or symptomatic desmoid tumors. It is hypothesized that the combination will provide long-lasting disease control and a quick time to treatment response.

This phase 2 study will enroll participants \geq 18 years of age. The pharmacokinetics (PK) and optimal dosing of nirogacestat in younger participants has not been established.

Treatment will consist of a 3-month lead-in period of nirogacestat, followed by cryoablation procedure (single treatment), followed by continued nirogacestat treatment for up to a total of 24 months (maximum 26 cycles of treatment), unless disease progression or one of the criteria in Section 3.7 (Subject Study Completion or Termination) occurs. The lead-in period will allow assessment of the response to nirogacestat-alone and potentially lead to improved cryoablation success if there is tumor shrinkage.

In order to assess increased efficacy of combination therapy over single-modality cryoablation, results will be compared to historical data from the Stanford existing cryoablation population treated at Stanford. For these subjects, two-thirds are unable to be completely ablated and most of those patients will have clearly recurrent disease at 6 months. Therefore, we hypothesize that adding on nirogacestat to cryoablation will lead to an 80% clinical benefit rate at 1 year.

Nirogacestat alone has a RECIST response of 29% of patients at a median of 24 months.¹ At 1 year, the ORR was 2 of 17 (12%).

To evaluate effects of cryoablation plus nirogacestat on quality of life (QOL), we will collect patient-reported outcome (PRO) measures using the EQ-5D-3L.

To remain consistent with prior inclusion criteria for desmoid trials, we will only include subjects with growing or symptomatic desmoid tumors. In addition, we will standardize the cryoablation procedure by limiting subjects to 1 cryoablation treatment session at time of intervention and desmoid tumors that can be at least 50% treated with cryoablation but are $<$ 75% cryoablitable.

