10.2. Study Endpoints and Analyses

10.2.1. Primary Endpoint and Analysis

10.2.1.1. Primary Endpoint

The clinical benefit rate (CBR) is defined as the number and proportion of participants who are assessed with either a complete response (CR), a partial response (PR), or stable disease (SD) prior to 1 year after treatment start and show no evidence of loss of response nor progression

within that year. Response and progression will be assessed according to the Revised Response Evaluation Criteria in Solid Tumors (RECIST) v1.1.

10.2.1.2. **Primary Analysis Plan**

The primary analysis will be the calculation of the clinical benefit rate, (CBR), defined as the percentage of subjects in the analysis population who achieve a complete response (CR), partial response (PR), or stable disease (SD) as measured at 12 months \pm 1 month (approximately 1 year) from the start of treatment. CR, PR, and SD are as defined by RECIST v1.1. (See Appendix C RECIST v1.1). The CBR and the two-sided 95% Clopper-Pearson (exact) confidence interval will be calculated.

The analysis population will include all subjects who started nirogacestat and underwent cryoablation. Subjects who withdraw from the study prior to start of treatment or before receiving cryoablation and completing 1 year of treatment will be replaced.

10.2.1.3. **Relevant Subset for Primary Objective and Endpoint**

Evaluable subjects are those subjects who have received cryoablation therapy and completed 1 year of treatment.

10.2.1.4. **Primary Objective and Endpoint Assessment Methods**

CBR will be evaluated on the basis of clinical response as measured using imaging by MRI scan and evaluated by RECIST v1.1 (Appendix C). Determination of response will be made by the treating investigator.

10.2.1.5. **Measurement Time Points for Primary Objective / Outcome**

Imaging will be performed at screening, then every 3 cycles (ie, every 12 weeks \pm 14 days) until End of Treatment. MRI scan will be used at screening and at subsequent time points.

10.2.2. **Secondary Endpoints and Analysis**

10.2.2.1. **Clinical Benefit Rate (CBR) assessed by modified RECIST**

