For tumors with MRI enhancement, CBR will be evaluated on the basis of clinical response as measured using imaging by MRI scan and evaluated by modified RECIST (Appendix D). Determination of response will be made by the treating investigator. Imaging will be performed at screening, then every 3 cycles (ie, every 12 weeks \pm 14 days) until End of Treatment. MRI scan will be used at screening and at subsequent time points.

10.2.2.2. **Median Progression-free Survival (PFS)**

Median progression free survival (PFS) will be measured using imaging by MRI scan and evaluated by RECIST v1.1, mRECIST, and volumetrically (change in tumor volume as assessed by MRI volumetric).

Progression-free survival is defined as the time from start of treatment to date of progression or death due to any cause. If a subject is not known to have progressed or died, then PFS will be censored at the latest date the subject was known to be alive or progression-free (on or before the cut-off date). The PFS distribution will be estimated using the Kaplan-Meier method, and

the Kaplan-Meier curves, medians and 95% confidence intervals of the medians will be presented.

10.2.2.3. **Objective Response Rate (ORR) at 1 year**

For the objective response rate (ORR) at 1 year, the percentage of subjects who start study treatment and achieve an objective response (CR or PR) will be calculated. ORR will be measured using imaging by MRI scan and evaluated both RECIST v1.1, mRECIST, and MRI volumetric.

The ORR will be calculated as the proportion of subjects with objective response. The ORR and the two-sided 95% Clopper-Pearson (exact) confidence interval will be calculated.

10.2.2.4. **Time to Response (TTR)**

Time to response is defined as the time from the start of treatment with nirogacestat to the first objective tumor response (CR or PR), and will be measured using imaging by MRI scan and evaluated by RECIST v1.1, mRECIST, and volumetrically.

The TTR distribution will be estimated using the Kaplan-Meier method, and the Kaplan-Meier curves, medians and 95% confidence intervals of the medians will be presented.

10.2.2.5. **Duration of Response (DoR)**

Duration of response (DoR) is defined as the time from the date of documented disease response (CR or PR) to the date of the first documented progression, and will be determined using imaging by MRI scan and evaluated by RECIST v1.1, mRECIST, and volumetrically.

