10.4.4. Criteria for Future Studies

With our total sample size of 20, we will reject the null hypothesis and conclude that the treatment is efficacious if the number of responses is ≥ 11 . Otherwise, we will conclude that that the treatment is not promising.

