13.4. Appendix D. Modified RECIST (mRECIST)¹⁰

FORMULA

Responses are defined as the following (RECIST is listed for comparison):

	RECIST	mRECIST
Complete response	Disappearance of all target lesions	Disappearance of any intratumoral arterial enhancement in all target lesions
Partial response	At least a 30% decrease in the sum of diameters of target lesions, taking as reference the baseline sum of the diameters of target lesions	At least a 30% decrease in the sum of diameters of viable (enhancement in the arterial phase) target lesions, taking as reference the baseline sum of the diameters of target lesions
Stable disease	Any cases that do not qualify for either partial response or progressive disease	Any cases that do not qualify for either partial response or progressive disease
Progressive disease	An increase of at least 20% in the sum of the diameters of target lesions, taking as reference the smallest sum of the diameters of target lesions recorded since treatment started	An increase of at least 20% in the sum of the diameters of viable (enhancing) target lesions, taking as reference the smallest sum of the diameters of viable (enhancing) target lesions recorded since treatment started

<https://www.mdcalc.com/modified-response-evaluation-criteria-solid-tumors-mrecist#evidence>

Modified RECIST criteria were proposed to address scenarios where treatment did not result in overall tumor shrinkage but did cause intratumoral necrosis, reducing viable tumor. Tumor response after ablation will also include assessment by modified RECIST guidelines to incorporate measurements of viable tumor. Similar to RECIST, target lesions must appear suitable for accurate and repeat measurements, and have a diameter of 1 cm or more, while non-target lesions have diameter < 1 cm. At baseline and follow up imaging, measurement of the longest viable tumor diameter should not include any major intervening areas of necrosis. Multiphasic post-contrast imaging will be available; the radiologist will choose the phase of imaging for measurement that best delineates the viable tumor component. If there are multiple intratumoral areas of enhancing viable tumor surrounded by areas of necrosis within the same target lesion, only the longest viable tumor diameter should be captured, again avoiding the

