inclusion of any major intervening areas of necrosis. For evaluation by mRECIST, CR is defined by absence of enhanced areas in target lesions; PR and PD as the same degree of decrease and increase as in the RECIST criteria, with sums of diameters of enhanced areas in target lesions rather than sums of diameters of the whole target lesions size; and SD as neither PR or PD.¹¹⁻¹⁶

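### The 50% null rate comes from mRECIST recurrence but is tested on RECIST v1.1 clinical benefit, so rejecting it does not by itself show improvement over subtotal cryoablation alone

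*Protocol*

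**What the plan says.** **Source of the null.** Protocol section 10.4.3 sets the null 1-year CBR at 50%. It rests this on clinical experience with subtotally cryoablated desmoids, which are said to have a more than 50% "chance of recurrence at 1 year; determined using mRECIST".

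**What is tested.** Section 10.2.1.1 defines the primary CBR by the other criterion: "Response and progression will be assessed according to the Revised Response Evaluation Criteria in Solid Tumors (RECIST) v1.1". Section 10.4.2 sizes the trial for that endpoint with P0 = 0.5, P1 = 0.8 and a one-sided exact test at 0.05: "The results assume that population proportion under the null hypothesis is 0.5". Section 10.4.4 sets the decision: "we will reject the null hypothesis and conclude that the treatment is efficacious if the number of responses is" at least 11 of 20.

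**How the criteria differ.** Appendix D (section 13.4) adds mRECIST because the treatment is ablative: "Tumor response after ablation will also include assessment by modified RECIST guidelines to incorporate measurements of viable tumor". It defines mRECIST PR and PD "with sums of diameters of enhanced areas in target lesions rather than sums of diameters of the whole target lesions size". CBR by mRECIST is a separate secondary endpoint, which section 10.2.2.1 restricts: "For tumors with MRI enhancement, CBR will be evaluated on the basis of clinical response".

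**The intended comparison.** Section 1.1 says results will be compared with the institution's historical cryoablation patients, to assess the gain of the combination over cryoablation alone. It says of those patients that "two-thirds are unable to be completely ablated and most of those patients will have clearly recurrent disease at 6 months", and names no criterion.

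**The concern.** A single-arm test has the meaning of its null rate. Here that rate is presented as what subtotal cryoablation achieves alone, but it was read on one scale and is applied to an endpoint on another.

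The difference matters in this trial in particular. Every eligible tumor is 50 to <75% ablatable and the cryoablation is subtotal by design (sections 3.1.1 and 4.2), so non-enhancing tissue inside the target lesion is to be expected. The whole-lesion diameter and the enhancing diameter can then classify the same patient differently as stable or progressing. If the RECIST v1.1 rate for cryoablation alone is not 50%, rejecting 50% answers a different question from whether the combination beats cryoablation alone.

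**Working it through.** **1. Inputs.** n = 20, P0 = 0.5, P1 = 0.8, one-sided exact test, alpha 0.05, stated power 100.0% (section 10.4.2); cut-off ≥11 (section 10.4.4). The 1-year RECIST v1.1 CBR after subtotal cryoablation alone is not in the protocol. Below it is called b and given an assumed range of 0.40 to 0.70.

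**2. The plan's own figure.** Under the exact test the rejection probability is P(X ≥ k | n, p), the sum over x = k to n of C(n,x) p^x (1−p)^(n−x).

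- k = 14: 0.0577 at p = 0.5, above 0.05.
- k = 15: 0.0207 at p = 0.5, and 0.8042 at p = 0.8.
- k = 11: 0.4119 at p = 0.5, and 0.9974 at p = 0.8.

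The smallest valid 5% cut-off is therefore ≥15, with 80% power. The stated 100.0% is approached only with the ≥11 rule, whose type I error at 0.5 is 41%. That is a separate error. From here the valid cut-off of ≥15 is used, to show what remains once it is corrected.

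**3. Size of the test.** For H0: P ≤ 0.5 with ≥15 of 20, the maximum rejection probability under the null is 0.0207, whatever the source of 0.5. The mismatch does not change it.

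**4. Meaning of a rejection.** Suppose the combination were no better than cryoablation alone on the RECIST v1.1 scale, so the true CBR equals b. The chance of rejecting with ≥15 of 20 is:

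| assumed b | 0.40 | 0.45 | 0.50 | 0.55 | 0.60 | 0.65 | 0.70 |
|---|---|---|---|---|---|---|---|
| P(X ≥ 15) | 0.0016 | 0.0064 | 0.0207 | 0.0553 | 0.1256 | 0.2454 | 0.4164 |

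Solving P(X ≥ 15 | 20, b) = 0.05 gives b = 0.544, a 1-year failure rate of 1 − 0.544 = 45.6%.

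**5. The other direction.** If b were 0.40, a cut-off of ≥13 would hold alpha at 0.0210 with power 0.9679 at 0.8. Using ≥15 gives power 0.8042, so the cost is then lost power.

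**6. Cut-offs for an mRECIST test against 0.5.** Since section 10.2.2.1 limits mRECIST CBR to enhancing tumors, the number assessable may be below 20. The smallest valid cut-offs are:

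| assessable | cut-off | alpha at 0.5 | power at 0.8 |
|---|---|---|---|
| 20 | ≥15 | 0.0207 | 0.8042 |
| 19 | ≥14 | 0.0318 | 0.8369 |
| 18 | ≥13 | 0.0481 | 0.8671 |
| 17 | ≥13 | 0.0245 | 0.7582 |
| 16 | ≥12 | 0.0384 | 0.7982 |

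**The case against.** **The test's size does not depend on where 0.5 came from.** This stands. A reader might infer that the trial's type I error is inflated by the mismatch. The documents do not support that: the stated null is P ≤ 0.5, and an exact test with a valid cut-off holds its level for that null.

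**The benchmark may already be conservative.** Recurrence above 50% puts the mRECIST CBR below 0.5. Section 1.1 reports recurrence at 6 months in most incompletely ablated patients, and section 1.2.1 calls recurrence or progression inevitable after incomplete ablation. This stands in part. It makes b of 0.6 or 0.7 look unlikely, but the margin is unquantified. The first figure is on the mRECIST scale, and the other two name no criterion.

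**RECIST v1.1 CBR is probably the higher of the two.** One might argue that a whole lesion can look stable while enhancing tumor regrows. That is plausible from Appendix D, but the protocol gives no data on it, so no direction is claimed here.

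**Section 10.4.4 concludes only that the treatment is efficacious or not promising.** True; it does not name cryoablation as the comparator, and the synopsis lists nirogacestat alone as a second historical control. But section 10.4.3 ties P0 to subtotal cryoablation and section 1.1 gives that comparison as a purpose, so readers will take a rejection that way.

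**mRECIST CBR is already a secondary endpoint.** It is, and that makes the repair cheap. It might tempt one to let an mRECIST test decide the comparative claim. That would go too far, because it would change the decision endpoint and leave other differences from the historical group:

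- The trial clock starts with nirogacestat. Cryoablation follows three 28-day cycles (84 days), so 1 year is about 365 − 84 = 281 days after ablation. The start of the historical clock is not stated.
- Historical recurrence is not shown to be the complement of CR + PR + SD without loss of response.
- Section 10.2.1.3 requires evaluable subjects to have completed 1 year of treatment. No such selection is described for the historical patients.

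**Conclusion.** The mismatch is explicit in the text: P0 was determined by mRECIST and is tested on RECIST v1.1 CBR, with no bridging rate. Rejecting 50% remains a valid statement about P ≤ 0.5 once the cut-off is valid, but does not by itself show improvement over subtotal cryoablation alone.

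The size of the problem cannot be fixed from the protocol. The illustration says that with ≥15 of 20 the chance of a rejection without any gain over cryoablation passes 5% when the RECIST v1.1 benchmark exceeds 0.544; below 0.5 the cost is power. This assumes 20 evaluable subjects, independent outcomes and a cut-off the protocol does not currently use. The higher benchmarks in the table are assumptions, not estimates. The point concerns the justification and reading of the null, and should be corrected, but it does not overturn the design.

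**What to change.** 1. Keep CBR by RECIST v1.1 as the primary endpoint, with its exact confidence interval.
2. Prespecify a supportive one-sided exact test of the mRECIST CBR against the mRECIST-derived 50%, with the cut-off set by the number of enhancing tumors assessable: ≥15/20, ≥14/19, ≥13/18, ≥13/17 or ≥12/16.
3. State in sections 10.4.3 and 10.4.4 that P0 was derived by mRECIST, and that the RECIST v1.1 test against 50% does not alone support superiority to subtotal cryoablation. Call the mRECIST test supportive, and name the remaining differences from the historical group (start of the clock, definition of recurrence, completion of 1 year of treatment).
4. If a RECIST v1.1 historical rate is already available, restate P0 from it and recompute. For 20 subjects and a true CBR of 0.8:

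| P0 | cut-off | alpha | power |
|---|---|---|---|
| 0.40 | ≥13 | 0.0210 | 0.9679 |
| 0.45 | ≥14 | 0.0214 | 0.9133 |
| 0.50 | ≥15 | 0.0207 | 0.8042 |
| 0.55 | ≥16 | 0.0189 | 0.6296 |
| 0.60 | ≥17 | 0.0160 | 0.4114 |

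Items 1 to 3 cost one extra analysis of data already collected and a narrower claim. Item 4 may cost power: at a restated P0 of 0.55 it falls to 63%.

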10.4.4. Criteria for Future Studies

With our total sample size of 20, we will reject the null hypothesis and conclude that the treatment is efficacious if the number of responses is ≥ 11 . Otherwise, we will conclude that that the treatment is not promising.

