Statistical Considerations	
Descriptive statistics (response rate, time to response, progression-free survival). Comparison to historical controls of nirogacestat alone and Stanford-treated cryoablation patients.
 
The primary outcome is clinical benefit rate (CR + PR + SD) at 1 year. We plan to enroll a total of 20 subjects. Assuming a null CBR of ≤ 0.5 versus an alternate CBR of 0.8, we have a maximum statistical power of 100.0% to detect a difference of 0.3 using a one-sided exact test with a type 1 error of 0.05.

Study Duration	
Duration of treatment for a subject via this study protocol is up to 24 months (26 cycles of treatment). This study will be complete when the last study data, including follow-up, has been collected, and analysis is complete. The duration of enrollment for this study will be approximately 25 months (including the initial 28-day screening period). Based on the determination of clinical benefit after 12 months' treatment, and 3 months for analysis of the primary endpoint, preliminary results for the primary endpoint are expected to be available approximately 40 months from the start of enrollment. Based on 25 months to completely enroll, and overall individual treatment period of approximately 24 months, the overall period until treatment is complete will be about 49 months from the start of enrollment. The complete final analysis (including primary and secondary analyses and safety assessments) and termination of all study activities is expected to be at about 53 months.
 
Key milestones are as follows.
 
• The per-subject screening period is approximately 28 days.• The duration of enrollment (minus the screening period) is approximately 24 months.• The per-subject primary endpoint (clinical benefit) is assessed after 12 months' treatment.• The per-subject duration of treatment is approximately 24 months (26 cycles of treatment).• Final subject visit is about 30 days after last treatment.• Nominal duration of subject participation is up to about 26 months.• Final study analysis is expected to take about 3 months.
Subject Duration	Approximately 26 months (28-day screening period, approximately 24 months of treatment, and End of Treatment visit about 30 days after last study treatment).

PROTOCOL SCHEMA

Subject Consent

Screening (Day 1 to Day 28):

(Collect archival histology report, EQ-5D-3L questionnaire, ECG, serum pregnancy test, routine labs & scans).

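### The success rule of 11 or more out of 20 carries a 41% type I error, not 5%; the exact 5% test the protocol names needs 15 of 20 and has 80.4% power, not 100.0%.

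*Protocol*

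**What the plan says.** Section 10.4.2 of the Protocol takes a null clinical benefit rate of 0.5 and an alternative of 0.8. It tests them "using a one-sided exact test at an alpha level of 0.05" and concludes: "Our sample size of 20 achieves 100.0% power to detect a difference" of 0.3. It adds: "Power was also computed using the normal approximation method". The Statistical Considerations row of the Synopsis repeats the claim: "we have a maximum statistical power of 100.0% to detect a difference of 0.3 using a one-sided exact test", with the type I error again given as 0.05.

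Section 10.4.4 turns this into a decision. With 20 subjects, "we will reject the null hypothesis and conclude that the treatment is efficacious if the number of responses is" 11 or more. Any lower count is read as not promising.

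Section 10.2.1.2 plans to report the rate with a two-sided 95% Clopper-Pearson interval. Section 10.3 plans no interim analysis. Section 10.4.1 allows up to 23 enrolled subjects to reach 20 evaluable.

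**The concern.** Eleven of 20 is an observed rate of 55%, only one subject above the count expected if the true rate is the null value of 50%. A cut-off that close to the null mean cannot belong to a 5% test. Separately, 20 binary observations cannot give essentially certain detection of 80% against 50% at that level.

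Section 10.4.4 holds the protocol's only numerical success criterion. If it is applied as written, a combination no better than the 50% benchmark for subtotal cryoablation has a large chance of being declared efficacious and carried forward. The stated power also misinforms anyone judging whether 20 subjects are enough for the test the protocol names.

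**Working it through.** **Inputs.** P0 = 0.5, P1 = 0.8, n = 20, one-sided exact test, alpha 0.05 (Section 10.4.2 and Synopsis). Cut-off r = 11 (Section 10.4.4).

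**Formula.** With X ~ Binomial(20, p), P(X ≥ r | p) = Σ from x = r to 20 of C(20, x) p^x (1 − p)^(20 − x). Type I error uses p = 0.5 and power uses p = 0.8.

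**1. Trying to reproduce the stated 100.0%**

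| Reject at or above | Type I error (p = 0.5) | Power (p = 0.8) |
|---|---|---|
| 10 | 0.5881 | 0.9994 |
| 11 (as written) | 0.4119 | 0.9974 |
| 12 | 0.2517 | 0.9900 |
| 13 | 0.1316 | 0.9679 |
| 14 | 0.0577 | 0.9133 |
| 15 | 0.0207 | 0.8042 |
| 16 | 0.0059 | 0.6297 |

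The stated power is not reproduced for a 5% test. It is approached only by rules that abandon the 5% level. The written rule has 99.7%.

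**2. Type I error of the written rule.** At p = 0.5 the distribution is symmetric, so P(X ≥ 11) = (1 − P(X = 10))/2. P(X = 10) = 184,756/1,048,576 = 0.1762, which gives (1 − 0.1762)/2 = 0.4119.

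**3. Cut-off of the exact 5% test.** The numbers of outcomes for 15 to 20 successes are 15,504 + 4,845 + 1,140 + 190 + 20 + 1 = 21,700. So P(X ≥ 15 | 0.5) = 21,700/1,048,576 = 0.0207. Adding C(20, 14) = 38,760 gives 60,460/1,048,576 = 0.0577, which exceeds 0.05. The cut-off is therefore 15.

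**4. Power at that cut-off.** P(X ≥ 15 | 0.8) = 0.8042.

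**5. Normal approximation, the second method cited.** Power = Φ[(0.3·√20 − 1.645·√0.25)/√0.16] = Φ[(1.3416 − 0.8224)/0.4] = Φ(1.298) = 0.903. With continuity correction, 0.3 becomes 0.3 − 1/40 = 0.275, and the result is Φ[(1.2298 − 0.8224)/0.4] = Φ(1.0185) = 0.846. Other variance choices and the arcsine form give between 85.0% and 95.6%. None gives 100.0%.

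**6. Sample size at which 100.0% would be true.** The exact one-sided 5% test of 0.5 against 0.8 first reaches 99.95% power at n = 58 (cut-off 36). Power does not rise smoothly with n, so this figure only illustrates the distance from 20.

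**7. Consistency with the planned interval.** Two-sided 95% Clopper-Pearson limits:

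- 11/20: 31.5% to 76.9%.
- 12/20 and 13/20: lower limits 36.1% and 40.8%.
- 14/20: 45.7% to 88.1%.
- 15/20: 50.9% to 91.3%.

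The interval first excludes 50% at 15, the same cut-off as the exact test.

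**The case against.** Four points can be made for the protocol.

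- **The two headline figures belong to different rules.** The 41.2% is the type I error of the written rule, whose power is 99.7%. The 80.4% is the power of the declared 5% test, whose type I error is 2.1%. This is correct and should be kept in view. Under the written rule the chance of missing a true 80% is about 0.3%, so the harm of the rule as written is false positives; the roughly 20% miss rate belongs to the declared test. The contradiction remains, because the protocol claims 5% and 100.0% together and no cut-off at n = 20 delivers both.
- **The rule sits under a heading about future studies, and the primary analysis is an estimate with an interval.** A reader of 11/20 would also see 31.5% to 76.9%. That softens the practical consequence. It does not excuse the rule, because Section 10.4.4 explicitly rejects the null and concludes efficacy, and no type I error other than 0.05 is stated anywhere.
- **A separate SAP might use the right cut-off.** It would then contradict the protocol. The fault is wrong numbers in the text, not missing detail.
- **Fifteen is not the only remedy.** The sponsor could declare a cut-off of 14 with a type I error of 5.8% and power of 91.3%, or enlarge the trial. That is fair. Fifteen follows only if n = 20 and alpha 0.05 are both kept.

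**Conclusion.** The concern holds and must be fixed. On the protocol's own inputs the written rule has a type I error of 41.2%, about eight times the declared 5%. The declared exact test rejects at 15 or more, with an attained type I error of 2.1% and power of 80.4% rather than 100.0%. The normal approximation does not rescue the stated power. Results of 11, 12, 13 or 14 of 20 would be called efficacious although the planned interval includes the null rate. If the true rate is 50%, those four results together have probability 0.4119 − 0.0207 = 0.3912.

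These figures assume exactly 20 analysed subjects with independent outcomes, and the null and alternative rates given in Section 10.4.2. No outside figure is used.

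**What to change.** Keeping n = 20 and alpha 0.05:

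1. In Section 10.4.4, replace the cut-off of 11 with 15 of 20.
2. In Section 10.4.2 and the Synopsis, replace 100.0% with 80.4% power, and state the attained one-sided type I error of 2.1%.
3. Because up to 23 subjects may be enrolled, give the exact cut-off for other analysed numbers: 15 of 21 (type I error 3.9%, power 89.1%), 16 of 22 (2.6%, 86.7%) and 16 of 23 (4.7%, 92.8%).

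If 80.4% power is judged too low, the sponsor should decide now on a larger number of evaluable subjects, or openly declare a different alpha, before outcomes are known.

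**Cost.** Text changes in three places, made through a protocol modification approved under Section 9.1. No extra patients and no change to treatment or assessments. The change is substantive, though: the observed rate needed for success rises from 55% (11/20) to 75% (15/20), and the stated power becomes less favourable.

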10.4. Sample Size

10.4.1. Accrual estimates

Stanford sees approximately 30 to 40 adult subjects annually in the Sarcoma Clinic with desmoid tumor. This study will enroll up to 23 subjects, in order to achieve 20 evaluable subjects. It is estimated that approximately 23 subjects can be enrolled within 24 months at Stanford University.

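### The only go rule is a count for 20 subjects, but the primary analysis population can hold 21 to 23; the printed 11 misses the stated 5% at every one of these sizes, and correcting it to 15 need not hold 5% at 22 or 23

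*Protocol*

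**What the plan says.** - **Decision rule (Section 10.4.4).** For a total sample of 20, "we will reject the null hypothesis and conclude that the treatment is efficacious if the number of responses is ≥ 11"; otherwise the treatment is judged not promising. No other sample size is covered.
- **Design test (Section 10.4.2 and Synopsis).** "Assuming a null CBR of ≤ 0.5 versus an alternate CBR of 0.8", tested "using a one-sided exact test at an alpha level of 0.05". On power: "Our sample size of 20 achieves 100.0% power to detect a difference" of 0.3.
- **Denominator (Section 10.2.1.2).** "The analysis population will include all subjects who started nirogacestat and underwent cryoablation". A completed year of treatment is not required.
- **Replacement (Section 10.2.1.2).** Subjects who withdraw before treatment starts, or "before receiving cryoablation and completing 1 year of treatment will be replaced".
- **Evaluable (Section 10.2.1.3).** Both cryoablation and a full year of treatment are needed.
- **Accrual (Section 10.4.1).** "This study will enroll up to 23 subjects, in order to achieve 20 evaluable subjects".
- **Estimate (Section 10.2.1.2).** "The CBR and the two-sided 95% Clopper-Pearson (exact) confidence interval will be calculated".

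**The concern.** The count, the denominator and the replacement rule are all fixed in the protocol, and they do not fit together. Take a subject who has cryoablation after Cycle 3 and withdraws at month 6. That subject is not evaluable, so another is enrolled to reach 20. The same subject did start nirogacestat and did have cryoablation, so remains in the denominator. One to three such cases give N = 21 to 23. Losses of this kind are foreseeable: the allowance of 23 for 20 anticipates them, and Section 1.2.4 reports that 16 of 69 nirogacestat patients (23%) in the phase 3 trial had adverse events leading to treatment discontinuation.

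At stake is the trial's only efficacy conclusion. A count that is too low at N = 20 becomes lower still, relative to the null, as N grows. A sponsor who corrected only the count at 20 could still be left with a test above its stated error rate.

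**Working it through.** **Inputs.** P0 = 0.5, P1 = 0.8, one-sided exact alpha 0.05, n = 20 (Section 10.4.2); count 11 (Section 10.4.4); enrolment cap 23 (Section 10.4.1).

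**Formulas.** With X binomial(N, p), the null rate of a count c is the sum over x ≥ c of C(N, x) × 0.5^N. Power is the sum over x ≥ c of C(N, x) × 0.8^x × 0.2^(N−x). The exact cut-off is the smallest c whose null rate is at most 0.05.

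**Step 1: the plan's own figure at N = 20.**
- Count 11: null rate = 0.5 × (1 − C(20,10)/2^20) = 0.5 × (1 − 184,756/1,048,576) = 0.412. Power is 99.7%.
- Count 14: null rate 0.058, too high. Count 15: 21,700/1,048,576 = 0.021, with power 80.4%. The exact 5% test therefore needs 15.
- Normal approximation, one-sided, null variance in the critical value: (0.3 − 1.645 × √(0.25/20)) / √(0.16/20) = 1.30, giving 90.3%. With the alternative variance it is 95.6%. Two-sided and continuity-corrected variants run from 73% to 92%.

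The stated 100.0% is not reproduced by any 5% test. It lies close to the power of the printed count of 11, whose type I error is 0.412.

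**Step 2: N = 20 to 23, every subject able to count as a response.**

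| N | 11/N | Null rate, ≥11 | Null rate, ≥15 | Null rate, ≥16 | Exact 5% cut-off | Power at cut-off |
|---|---|---|---|---|---|---|
| 20 | 55.0% | 0.412 | 0.021 | 0.006 | 15 | 80.4% |
| 21 | 52.4% | 0.500 | 0.039 | 0.013 | 15 | 89.2% |
| 22 | 50.0% | 0.584 | 0.067 | 0.026 | 16 | 86.7% |
| 23 | 47.8% | 0.661 | 0.105 | 0.047 | 16 | 92.9% |

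A count of 15 holds 5% at 20 and 21 but not at 22 or 23. A count of 16 holds it throughout, with power 63.0% at N = 20 and 76.9% at N = 21.

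**Step 3: N below 20**, possible if more than three of the 23 are lost before cryoablation.
- N = 17: cut-off 13 (3,214/131,072 = 0.025; a count of 12 gives 9,402/131,072 = 0.072).
- N = 18: cut-off 13 (12,616/262,144 = 0.048; a count of 12 gives 31,180/262,144 = 0.119).
- N = 19: cut-off 14 (16,664/524,288 = 0.032; a count of 13 gives 43,796/524,288 = 0.084).

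**Step 4: sensitivity to how withdrawals count.** Suppose the one to three extra subjects can never be responses and the other 20 respond at 0.5. The number of responses is then binomial(20, 0.5) whatever the denominator. A count of 15 keeps 0.021, and a count of 11 keeps 0.412.

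**The case against.** **Most of the size belongs to the wrong count, not to the moving denominator.** This stands. A count of 11 has a null rate of 0.412 at N = 20 with no replacement at all. The denominator is a second defect that adds to it.

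**The excess at 22 and 23 rests on an assumption.** This stands as a condition. Section 10.2.1.2 counts response as measured at 12 months ± 1 month, so a withdrawn subject without that scan may not count, and Step 4 then applies. The figures 0.067 and 0.105 apply where withdrawn subjects are followed and can still count, which Sections 3.7.2 and 3.7.3 allow for subjects who stop treatment but permit follow-up.

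**The exact test is already specified, and cut-offs for the attained N could be left to an analysis plan.** This stands in part. Section 10.4.2 does name the test. But Section 10.4.4 prints a count that contradicts it, so the protocol has two rules that disagree.

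**The replacement sentence can be read more than one way.** True. The evaluable definition and the 23-for-20 allowance favour the reading used here.

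Three stronger readings should be resisted:
- A reader might infer that no fixed count can hold 5%. The 16-response column shows otherwise, at a cost in power.
- A reader might infer that the protocol would declare 11 of 23 efficacious, a rate below the null. Section 10.4.4 is worded for 20, so this extrapolates. Strictly, 21 to 23 are undefined.
- A reader might see an error in pairing a two-sided 95% interval with a one-sided 5% test. The interval is for estimation and is not the decision rule. Adding a 90% interval is a reporting preference.

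**Conclusion.** The point holds. The only go rule covers N = 20, while the protocol's own population and replacement rules allow 21 to 23. The printed count fails the stated one-sided 5% at N = 20 and does worse if carried further. This part needs no assumption beyond the design values and, for N above 20, that the count is carried over unchanged.

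Correcting the count to 15 settles N = 20 and 21. At N = 22 and 23 it leaves 0.067 and 0.105, on two assumptions: post-cryoablation withdrawals are replaced but kept in the denominator, and they can still count as responses. If they cannot, 15 stays within 5%. The protocol does not say which applies, so the error rate after correcting the count alone is not settled.

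**What to change.** 1. In Section 10.2.1.2, name one denominator for the primary test, reconcile it with the evaluable definition in Section 10.2.1.3, and say whether a subject who withdraws after cryoablation is replaced and how that subject counts.
2. In Section 10.4.4, replace the count with: H0 is rejected if the one-sided exact binomial p-value against 0.5, on the number in that population, is at most 0.05. Print the cut-offs:

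| N | 17 | 18 | 19 | 20 | 21 | 22 | 23 |
|---|---|---|---|---|---|---|---|
| Responses needed | 13 | 13 | 14 | 15 | 15 | 16 | 16 |

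3. Correct the power in Section 10.4.2 and the Synopsis to 80.4% at N = 20.

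The cost is a few sentences and one small table, with no patients and no new data. It should be done before the temporary data lock for the primary outcome described in Section 9.4.1. The downside is a stricter threshold and a lower stated power. If withdrawn subjects stay in the denominator but can never respond, the cut-off of 16 at N = 22 or 23 is conservative: it then acts on 20 potential responders, with null rate 0.006 and power 63.0%. This is why item 1 has to be settled with item 2.
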